### 6.0 Procedures Involved\*

**Type of study design.** We will conduct a six-week, individual randomized controlled trial with two arms. While recruitment is being conducted at various locations, the intervention is delivered remotely and all data collection and analyses will be conducted through Medstar Health Research Institute.

Individuals who express an interest in the study will be screened for eligibility by phone. Questionnaires will be completed in REDCap. Study staff will download screening results and calculate ISI scores. Participants will be notified of eligibility by phone or email within 3 business days of completing the eligibility screening.

If the participant is eligible and wishes to proceed with study enrollment, she will receive a personalized REDCap link by email with baseline forms. Study staff will be available to administer the forms by phone or to send hard copies by mail if the individual prefers. Prior to randomization we will collect information on basic demographics (e.g. age, body mass index, education, income, marital status), medical history (e.g. comorbidities, time since treatment, concurrent medication), and lifestyle habits (e.g. physical activity, smoking, alcohol consumption, diet) as well as our primary outcome of the Insomnia Severity Index (ISI). The ISI defines 'no clinically significant' insomnia as a score of 0-7, 'sub-threshold' insomnia as a score of 8-14, 'moderate severity clinical' insomnia a scores of 15-21, and 'severe clinical' insomnia as a score of 22-28.

## PROTOCOL TITLE: Testing mHealth Delivery of Cognitive Behavioral Therapy for Insomnia to Breast Cancer Survivors

**Randomization.** After screening for eligibility, participants will complete informed consent. Our biostatistics consultant will provide randomization assignments in a 1:1 allocation ratio using a block randomized design with random block sizes between 4-6.

During the study the Sleep Helper program will collect sleep diary data via voice in an ongoing manner. At the completion of the six-week intervention individuals will complete forms via a personalized REDCap link. If individuals complete >50% of the items on a scale mean substitution of missing values with respondent's average response on remaining scale items will be used.

This study will use Amazon Alexa Echo Dots. Participants will also receive a hotspot and a smartphone, so that they do not have to rely on personal wifi (thus further protecting their identity). These devices will be supplied to participants at no cost. We do not foresee any significant risk in using this device. This device is exempt from IDE regulation as it is in commercial distribution and is used in accordance with the indications in labeling.

**Data collection.** Baseline data before randomization will be collected from all participants using REDCap. We will have a separate link to a password protected recruitment document (with name and contact information) where unique study IDs will be assigned, thus further protecting the identity of participants. In the de-identified REDCap forms we will collect information on basic demographics (e.g. age, race/ethnicity, body mass index, education, marital status), medical history (e.g. comorbidities, time since treatment), and lifestyle habits (e.g. physical activity, alcohol consumption) as well as our primary outcome of the Insomnia Severity Index (ISI). Before randomization and upon completion of the intervention and control, participants will be administered surveys of relevant questions from the CSD through REDCap. We will collect basic sleep information including time getting into bed, time attempting to go sleep, time awake during the night, time awake in the morning, time getting out of bed, number of awakenings, and quality of sleep. We will also collect information on the PROMIS 29-item scale to see how co-occurring symptoms such as fatigue and anxiety are distributed by group. Additional information to be collected includes a morning/eveningness questionnaire to assess chronotype and participant expectations and motivations. All data will be self-reported.

Ongoing data collected through the Alexa app includes basic sleep information including time getting into bed, time attempting to go sleep, time awake during the night, time awake in the morning, time getting out of bed, number of awakenings, and quality of sleep. The ongoing data collected is used to inform treatment recommendations, but is not considered in the primary or secondary outcome analyses, which are based on the ISI and CSD.

Upon completion of the program, participants in the intervention arm will complete a system usability scale as well as a set of open-ended feedback questions after completion of the other REDCap forms.

### 7.0 Data and Specimen Banking\*

## **PROTOCOL TITLE: Testing mHealth Delivery of Cognitive Behavioral Therapy for Insomnia to Breast Cancer Survivors**

No specimens are being collected for the purposes of this study.

MHRI will maintain appropriate medical and research records for this trial, in compliance with ICH GCP and regulatory and institutional requirements for the protection of confidentiality of participants. As part of participating in a NIH-sponsored or NIH-affiliated study, each site will permit authorized representatives of the NIH, sponsor, and regulatory agencies to examine (and when permitted by applicable law, to copy) clinical records for the purposes of quality assurance reviews, audits, and evaluation of the study safety, progress, and data validity. Only trained study staff who need access to data for research purposes related to this project will have access to the data. Any data shared with Media Rez (software developer) will be deidentified.

### **Data Collection and Management Responsibilities**

Data collection will be the responsibility of the MHRI trial staff at the site under [name] supervision. [name] will be responsible for ensuring the accuracy, completeness, legibility, and timeliness of the data reported, as well as for storing all informed consent documents and for managing any other identifiable information, including any audio recordings or transcripts.

Data will be entered into REDCap, a 21 CFR Part 11-compliant data capture system provided by MHRI. The data system includes password protection and internal quality checks, such as automatic range checks, to identify data that appear inconsistent, incomplete, or inaccurate.

While participants will be recruited from multiple sites, all records will be collected and stored by MHRI and only MHRI research staff who have a need will be able to see identifiable information.

### **Study Records Retention**

Study documents will be retained for a minimum of 3 years after the last annual Federal Financial Report (FFR) is submitted.

### **8.0 Sharing of Results with Subjects\***

Individuals can view their own ongoing data in the app at any point in time. Data collected through REDCap will not be shared with those outside the research team and will only be reported in the aggregate.

### **Publication and Data Sharing Policy**

This study will be conducted in accordance with the following publication and data sharing policies and regulations:

## **PROTOCOL TITLE: Testing mHealth Delivery of Cognitive Behavioral Therapy for Insomnia to Breast Cancer Survivors**

National Institutes of Health (NIH) Public Access Policy, which ensures that the public has access to the published results of NIH funded research. It requires scientists to submit final peer-reviewed journal manuscripts that arise from NIH funds to the digital archive PubMed Central upon acceptance for publication.

This study will comply with the NIH Data Sharing Policy and Policy on the Dissemination of NIH-Funded Clinical Trial Information and the Clinical Trials Registration and Results Information Submission rule. As such, this trial will be registered at ClinicalTrials.gov, and results information from this trial will be submitted to ClinicalTrials.gov. In addition, every attempt will be made to publish results in peer-reviewed journals. Data from this study may be requested from other researchers 1 year after the publication of the primary endpoint by contacting [name] at Medstar Health Research Institute.

All ongoing monitoring or self-reported data will be available to participants at any time during the study via the app. To maintain patient engagement, we will send electronic study updates twice a year on study progress (enrollment, process data, etc). At the study conclusion, we will send an electronic newsletter to all involved patients who do not opt out with summary findings from the study.

### **9.0 Study Timelines\***

#### **9.1**

- Individuals will participate in the study for six weeks.
- We anticipate beginning recruitment for the study in late 2021, and enrolling the last participant by early 2023 (14 months total)
- We hope to complete the last data collection by Feb 2023, with analysis conducted by March 2023.

### **10.0 Inclusion and Exclusion Criteria\***

The research coordinator will contact potentially eligible participants by phone to discuss the study and conduct screening informed consent. Those who agree to be screened for eligibility will complete the screening questionnaire with the research coordinator by phone.

#### *Inclusion and Exclusion criteria*

##### **Inclusion Criteria**

In order to be eligible to participate in this study, an individual must meet all of the following criteria:

1. Willingness to maintain a consistent dosing pattern if currently taking sleep medications or using cannabis for sleep
2. Females; Age 18+
3. Self-reported or documented diagnosis of breast cancer stage I-III or stage IV ECOG 0-1
4. Completed curative treatment (surgery, radiation, chemotherapy) > 3 months prior to enrollment [ongoing adjuvant therapy permitted]
5. Has not undergone other behavioral sleep treatment within the prior 12 months

**PROTOCOL TITLE: Testing mHealth Delivery of Cognitive Behavioral Therapy for Insomnia to Breast Cancer Survivors**

6. Score greater than or equal to 8 on the Insomnia Severity Index
7. Able to understand and speak English

**Exclusion Criteria**

An individual who meets any of the following criteria will be excluded from participation in this study:

1. Diagnosed, untreated obstructive sleep apnea syndrome, narcolepsy, restless leg syndrome, periodic limb movement disorder, delayed sleep phase syndrome, central apnea
2. Bi-polar disorder, schizophrenia, initiation of psychological treatment within three months, alcohol or drug abuse in the prior year (Alcohol >2 drinks/day or consuming 5+ drinks in a single day in the prior month). (Moderate ADHD, depression and anxiety will not be exclusion criteria.)
3. Shift-work in the prior three months or anticipated during the study time
4. Planned regular travel out of time zone (>1 hour) during the study period.
5. Currently or planning to become pregnant during the study period

Indicate specifically whether you will include or exclude each of the following special populations:

- *Adults unable to consent- NO*
- *Individuals who are not yet adults (infants, children, teenagers)- NO*
- *Pregnant women- NO*
- *Prisoners- NO*

**11.0 Vulnerable Populations\***

N/A- We will not include adults who are unable to consent.  
We will not include individuals who are not yet adults.  
We will not include pregnant women.  
We will not include prisoners.

**12.0 Local Number of Subjects**

12.1 We plan to enroll up to 76 patients in the study total, with about one third accrued locally.

We anticipate screening approximately 150 women in order to identify n=76 for the RCT.

**13.0 Recruitment Methods**

We will only screen women over age 18 who have been identified as breast cancer survivors who completed treatment and self-report disrupted sleep. Thus, we anticipate that main reasons for ineligibility will be due to other criteria such as planned travel out of

**PROTOCOL TITLE: Testing mHealth Delivery of Cognitive Behavioral Therapy for Insomnia to Breast Cancer Survivors**

the time zone, ineligible ISI score (7 or less), or other diagnosed untreated sleep disorder such as sleep apnea.

We are using multiple recruitment sources as detailed below to facilitate rapid enrollment.

- a) Participants will be recruited from the Medstar Washington Hospital Center Cancer Institute, and Georgetown University's Lombardi Comprehensive Cancer Center. The research coordinator will screen daily patient appointment schedules coming in for routine medical oncology visits after treatment completion to determine which patients might be eligible for the study. With consent from the treating physician, the research coordinator will call potentially eligible participants by phone or arrange to meet them in person if preferred to discuss the study, conduct screening, and informed consent. We will also distribute study brochures to MedStar Health breast cancer clinics to reach out to survivors who report insomnia. If recruitment is slow, we will reach out to the other MedStar cancer clinics to determine if clinic-based recruitment is feasible.
- b) We will also reach out to local survivorship groups to distribute brochures, as was done in our previous studies of insomnia among BCS.
- c) We will recruit from the Georgetown Lombardi Comprehensive Cancer Center's Survey, Recruitment, and Biospecimen Collection Share Resource (SRBSR), which includes nearly 2,300 cancer survivors who have consented to be contacted for future research.
- d) We will recruit from the Susan Love Research Foundation Army of Women, a resource of 383,000 men and women interested in cancer research will also recruit participants. The recruitment flyer approved by Army of Women is attached to this application.
- e) Additional participants will be recruited from the Dana-Farber Cancer Institute (DFCI)/Harvard Cancer Center using procedures proven successful in previous studies. The DFCI team will use medical records to identify potentially eligible patients from the breast oncology clinics, and recruit them at the time of a scheduled outpatient visit. This clinic-based recruiting strategy previously accrued 56 adult survivors in a 12-month period. The DFCI team will use medical records to determine clinical eligibility (cancer diagnosis, age, and time since treatment) and will approach women at their regular clinic visit whether they have trouble sleeping that began or got worse after their breast cancer diagnosis. The screening checklist is included in this submission. Those who answer affirmatively to the basic screening questions will be referred to the MHRI team (via a private Box folder using a password protected spreadsheet) and submitting the completed screening form to administer the sleep screening questionnaire. The DFCI team will not collect data for this study after enrollment, and will not share medical records with the MHRI team.

All participants will receive a \$75 incentive through electronic gift card at the completion of the 6-week post-intervention forms. At study completion (once all participants have completed the study), those who completed the post-intervention forms will also receive an Amazon Dot device (no account linked) that they can keep for personal use.

## **PROTOCOL TITLE: Testing mHealth Delivery of Cognitive Behavioral Therapy for Insomnia to Breast Cancer Survivors**

Incentives will be delivered through an E-Gift card reward system, Tango. Tango provides instant delivery of their reward in which participants can redeem reward by visiting the website provided in their reward email to select the gift card of choice. Participants will have the option to either receive their gift card through email or can opt to receive their incentive in the form of a check delivered by mail to their home address. If participants opt to receive an e-gift card, they will receive an email to an address (supplied by the participant) with the subject line "Thank you for supporting research at MedStar Health Research Institute." The email contains the following language: "Your contributions to science are invaluable. MedStar Health Research Institute appreciates you taking the time to participate in one of our projects. Instructions to redeem will then be provided." A member of our research team will generate the incentives according to participant preferences.

To incentivize referrals for recruitment, incentives will be delivered through Tango to CBOs who refer individuals to the study. CBOs will receive \$50 for every individual who completes enrollment into the study and cites them as a referral source.

### **14.0 Withdrawal of Subjects\***

#### **DISCONTINUATION OF STUDY INTERVENTION/EXPERIMENTAL MANIPULATION**

When a subject discontinues using the Sleep Helper skill but does not withdraw from the study, remaining study procedures will be completed as indicated by the study protocol. The investigator or qualified designee will determine if any change in participant management is needed.

The data to be collected at the time of study intervention discontinuation will include the following:

- The reason(s) for discontinuing the participant from the intervention, and methods for determining the need to discontinue
- The participant will be asked to complete the post-interventions assessments, even though not participating in the intervention

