**4.1**

OBJECTIVES	ENDPOINTS
Primary	
To determine the impact of the voice-activated smart speaker CBT-I components on insomnia symptoms among breast cancer survivors using a randomized clinical trial.	We will collect data on the Insomnia Severity Index (ISI) total score pre- and post-intervention as our primary outcome. The ISI is a seven-item questionnaire with response categories from 0-4 (total score 0-28) asking about sleep patterns and specifically characterizing insomnia over the two weeks prior. The ISI defines 'no clinically significant' insomnia as a score of 0-7, 'sub-threshold' insomnia as a score of 8-14, 'moderate severity clinical' insomnia a scores of 15-21, and 'severe clinical' insomnia as a score of 22-28. Our clinically relevant target for success is to achieve sub-threshold or better scores ( $\leq 14$ ) among >80% of the intervention participants.
Secondary	
To determine differences in specific CSD metrics by intervention arm.	CSD Metrics: sleep efficiency, wake after sleep onset, sleep onset latency, total sleep time and sleep quality.
Tertiary/Exploratory	
To determine whether there are differences in ISI change by frequency of engagement or satisfaction with the intervention.	Among the intervention group we will also examine frequency of participant engagement and the system usability scale (SUS), including participant satisfaction with the program, and whether these factors affect ISI change.

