## 17.0 Data Management\* and Confidentiality

### ○ STATISTICAL HYPOTHESES

- Primary Endpoint(s): Insomnia Severity Index

We hypothesize that, compared to participants who receive a control intervention, participants who receive Cognitive Behavioral Therapy for Insomnia via the Sleep Helper skill will have lower ISI scores at the end of the six-week intervention. Alternatively, our null hypothesis is that there will be no difference in the ISI score between groups at the end of the six-week intervention. Thus our primary efficacy outcome is based on the continuous ISI scale. We plan to also conduct a categorical analysis: we further hypothesize that a greater percentage of those in the intervention arm will have a clinically significant reduction in ISI score to <14, or sub-threshold insomnia, than in the control arm.

- Secondary Endpoint(s): CSD Metrics

Our statistical objective is exploratory in that we are interested in whether we are seeing changes in metrics of the CSD. We will evaluate the following CSD metrics: sleep efficiency, wake after sleep onset, sleep onset latency, total sleep time and sleep quality.

- Exploratory Endpoint(s): We will analyze whether we see differences in ISI change by level of engagement and satisfaction with the intervention.

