#### Analysis of the Primary Endpoint(s)

The ISI is a seven-item questionnaire with response categories from 0-4 (total score 0-28) asking about sleep patterns and specifically characterizing insomnia over the two weeks prior. Our primary analysis endpoint will use this continuous ISI score.

We will test for assumptions of linearity of regression, homogeneity of error variances, independence of error terms, normality of error terms, and homogeneity of regression slopes. We will use analyses of covariance (ANCOVA) to compare the two groups, which controls for baseline ISI values. We will analyze the treatment effect using the intent-to-treat principle. Descriptive statistics will examine differences in baseline variables between completers and dropouts. If important differences are observed (suggesting the data are missing under a “Not Missing at Random” mechanism) or the loss to follow-up rate exceeds 10%, the primary analysis will be tested through multiple imputation of the ANCOVA model, where potential predictors of dropout will be included in the imputation model, e.g., response to a baseline question asking about the degree of motivation of the participants to stay in the study.

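### Section 14.0 gives two timings for the post-intervention ISI of a woman who stops Sleep Helper, so a primary-endpoint score could be taken early, in the intervention arm only

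*Combined protocol and SAP*

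**What the plan says.** Section 14.0 (Withdrawal of Subjects), under discontinuation of the study intervention, covers a participant who stops using the Sleep Helper skill without leaving the study. Its opening sentence says that "remaining study procedures will be completed as indicated by the study protocol". The next paragraph begins "The data to be collected at the time of study intervention discontinuation will include the following" and has two bullets. The first is the reason for stopping. The second is "The participant will be asked to complete the post-interventions assessments, even though not participating in the intervention".

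Elsewhere the post-intervention forms belong at six weeks:

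- Section 6.0, Randomization: "At the completion of the six-week intervention individuals will complete forms via a personalized REDCap link".
- Section 6.0, Data collection: the CSD questions are given on completion of the intervention and control conditions.
- Section 13.0: the incentive is paid "at the completion of the 6-week post-intervention forms".
- Section 17.0, Statistical Hypotheses: the intervention arm "will have lower ISI scores at the end of the six-week intervention".

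The endpoint table in section 4.1 names no week: "We will collect data on the Insomnia Severity Index (ISI) total score pre- and post-intervention as our primary outcome". Section 17.0 (Analysis of the Primary Endpoint) describes the ISI as "asking about sleep patterns and specifically characterizing insomnia over the two weeks prior".

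**The concern.** A coordinator who follows the opening sentence sends the ISI at week 6. One who follows the list sends it when the woman stops, which could be week 1 or 2. With a two-week recall period, a score taken then describes mostly or wholly the time before treatment or its first days.

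The rule is tied to the Sleep Helper skill. Controls use a website as they wish and have no defined discontinuation event, so early measurement can arise in one arm only. Intervention scores from various weeks would then be compared with week-6 control scores. The arms would differ in time for natural recovery and regression toward the mean, as well as in treatment.

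Nothing later in the plan would catch this. Loss to follow-up (section 14.0) requires that the post-intervention forms were not completed. A woman who completed them early is therefore not lost, adds nothing toward the 10% loss rate that triggers multiple imputation (section 17.0), and has no missing ISI to impute.

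**Working it through.** **Timing statements side by side**

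| Place | Timing of the post-intervention forms |
|---|---|
| 14.0, opening sentence | On the protocol schedule |
| 6.0, 13.0, 17.0 | End of six weeks |
| 14.0, list lead-in and second bullet | At the time of discontinuation |
| 4.1 | Post-intervention, no week named |

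The first two rows agree. The third, read literally, does not. The documents contain no assessment window, no repeat at week 6 after an early form, and no rule on how an off-schedule ISI enters the ANCOVA.

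**The plan's own figure.** Inputs from section 17.0 (Sample Size Determination): d = 0.65, pre-post correlation r = 0.5, two-sided alpha 0.05, 80% power. ANCOVA power comes from a noncentral t with ncp = d × √N / (2 × √(1 − r²)) and df = N − 3. At N = 58, ncp = 0.65 × 7.616 / (2 × 0.866) = 2.86 and power is 0.802. The stated N = 58 reproduces, and it does not depend on this point.

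**Illustration of size.** The documents give no rate of stopping Sleep Helper while staying in the study, no ISI standard deviation and no ISI time course. The following are therefore assumptions:

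- SD 5, so that d = 0.65 equals 0.65 × 5 = 3.25 points.
- Linear untreated improvement g = 3 points over six weeks (range 2 to 4).
- Early ISI at week t = 2.
- A share q of the intervention arm measured early.
- N = 76 (38 per arm), because women measured early do supply a score.

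Bias = q × g × (1 − t/6). Effective d = 0.65 − bias/5. With no early scores, power at N = 76 is 0.90.

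| q | Bias (points) | Effective d | Power, N = 76 |
|---|---|---|---|
| 20% | 0.2 × 3 × 0.667 = 0.40 | 0.57 | 0.81 |
| 30% | 0.3 × 3 × 0.667 = 0.60 | 0.53 | 0.75 |
| 40% | 0.4 × 3 × 0.667 = 0.80 | 0.49 | 0.68 |

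At 20%, the bias is 0.40/3.25 = 12% of the planned effect. Taking g from 2 to 4 points gives a bias of 0.27 to 0.53 point and power of 0.84 to 0.77.

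**Direction.** The table assumes that women measured early have not yet improved. A second calculation shifts the early scores by a fixed amount. At N = 76 with 20% measured early:

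- Early scores showing 0.325 SD less benefit than at week 6: d = 0.65 − 0.2 × 0.325 = 0.585, power 0.83.
- Early scores showing 0.325 SD more benefit: d = 0.715, power 0.94.
- No true six-week difference, early scores 0.325 to 0.65 SD better: the two-sided rejection rate is 0.062 to 0.099 rather than 0.05.

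Either sign is possible on what the documents give.

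**The case against.** The strongest reply is that the protocol fixes the timing elsewhere and that the second bullet is only loosely placed. On that reading it is not a data item like the reason for stopping. It is a reminder that she stays in follow-up and completes the usual six-week forms, which suits the intent-to-treat analysis. This reading is plausible, and it rules out saying that the protocol clearly instructs early measurement. It does not remove the conflict, because the lead-in still states a different time for the same forms.

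Four stronger readings are tempting, and the documents do not support them:

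- A reader might infer that an early ISI will be counted as the six-week score. No section says so. The plan only fails to exclude it.
- A reader might take 20-40% as the plan's own discontinuation rate. Those figures, in section 3.0, are dropout from web-based programs (up to 40%) and earlier CBT-I trials (20-30%). The women at issue here stop the skill, remain in the study and complete forms at that moment. The program is automated and remote, and no discontinuation visit is described, so they may be few.
- A reader might compute the loss at 29 per arm, where the same biases give power of 0.69, 0.63 and 0.56. That size already removes dropouts, while the mechanism requires that these women supply scores. 38 per arm is the consistent basis.
- A reader might conclude that the bias runs against the intervention. It reverses if women stop after an early gain.

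**Conclusion.** Section 14.0 contradicts itself on when a woman who stops Sleep Helper completes the post-intervention ISI. The literal reading of its list permits an early primary-endpoint score in one arm, with no window or off-schedule rule to contain it. This is a conflict between stated rules, not a clear instruction to measure early.

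Its size is unknown. On the assumptions above, 20% measured early moves the contrast by 0.4 point and power from about 0.90 to 0.81. Both the share and the direction are assumed. The planned sample size is unaffected. The wording should still be corrected, because the timing of the primary endpoint should not depend on which sentence a coordinator follows, and correcting it costs almost nothing.

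**What to change.** Reword section 14.0 so that only the date of and reason for stopping are recorded at discontinuation. State that the ISI, CSD and PROMIS-29 are collected in both arms at six weeks from a common start point, such as randomization, within a stated window. The window ensures that a form completed slightly early is not discarded.

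Add to the primary-endpoint analysis in section 17.0 that an ISI taken before the window is not used as the primary-endpoint value, though it may inform the imputation model, and that a woman with no ISI in the window counts as missing.

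The cost is a few sentences, with no added visits or participants. The downside is that some women may be harder to reach at week 6 than on the day they stop. The five-attempt contact procedure under loss to follow-up already addresses this.
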